5 SAMPLE SIZE CONSIDERATIONS

The sample size for this study was selected to detect frequent adverse events. Given a planned sample size of groups of 15 adults, toddlers, and younger children each receiving one of varying dose levels of ETVAX with or without dmLT, the study will have an approximately 80% and 90% chance of observing at least one serious adverse event or adverse event of special interest for events that occur at a rate of 10.3% and 14.3%, respectively. Additionally, if no serious adverse events are observed in 15 participants, the upper bound of the one-sided 95% confidence interval on the rate of serious adverse event occurrence is approximately 18%.

For infant cohorts with 30 participants per dose group, the study will have an approximately 80% and 90% chance of observing at least one serious adverse event or adverse event of special interest for events that occur at a rate of 5.3% and 7.4%, respectively. If no serious adverse events are observed in 30 participants, the upper bound of the one-sided 95% confidence interval on the rate of serious adverse event occurrence is approximately 9.5%.

For infant cohorts, with 30 participants per group, this study is designed to provide approximately 73% power to detect as low as a 2-fold difference in geometric mean fold rise (post-vaccination / baseline) between comparisons of two groups with varying doses of ETVAX and dmLT levels. This power calculation was based on the variability estimate, log10 standard deviation of 0.6, for CS6 obtained from a previous study of the vaccine in Sweden (VAC 003/OEV-121) and two-sample t-test using the 5% two-sided Type I error rate and 10% drop-out rate.

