6.8 Multiple Comparisons/Multiplicity

This is an exploratory study in descending age groups. Due to the exploratory nature of all of the statistical comparisons for immunogenicity endpoints, there will not be an adjustment for multiple comparisons across the entire study. However, within each immunogenicity endpoint for each age group, the Holm-Bonferroni correction for multiple testing will be applied to control the multiple comparisons associated with multiple treatment groups. It is acknowledged that there will be inflated Type I errors (i.e., inflated false statistical significances) from performing multiple unadjusted comparisons.

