8 IMMUNOGENICITY EVALUATION

The secondary and exploratory immunogenicity analyses are based on the ALS assay, ELISA assay and fecal assays. Whole blood and plasma specimens will be collected for immunogenicity assessments at Screening, Day 7 and Day 19. Fecal specimens will be collected for immunogenicity assessments at Screening, Day 1, Day 7, Day 19 and Day 29. All immunogenicity analyses will be conducted using the FA and the PP populations, unless they are the same. The number of participants in a population may vary by antigen and assay type as only participants contributing assessments will be included in the population for a specific antigen and assay. Individual participant data listings of immunogenicity will be presented in Listings 16.2.6.1(a)(b)(c)(d) - 16.2.6.3(a)(b)(c)(d) for ALS, fecal, and plasma, respectively.

Pairwise comparisons between each dose of the vaccine without dmLT, and each vaccine co-administered with dmLT adjuvant dose and placebo will be performed for each age-group: adults, toddlers (24-59 months), younger children (12-23 months), and infants (6-11 months). In addition, pairwise comparisons will be made between the combined vaccine without dmLT group and the combined vaccine with dmLT as well as comparisons of these two group with placebo.

Due to the hypothesis generating nature of multiple statistical comparisons for immunogenicity associated with multiple endpoints for this age and dose escalating study, all estimations will be carried out using a two-sided 5% Type I error rate. For each immunogenicity endpoint and antigen analyzed, a Holm's-Bonferroni correction will be applied to determine significance.

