LTB	Combined ETVAX without dmLT vs Combined ETVAX with dmLT	0.xxxx	0.xxxx	0.xxxx			
LIB	Placebo vs Combined ETVAX without dmLT	0.xxxx	0.xxxx	0.xxxx			
	Placebo vs Combined ETVAX with dmLT	0.xxxx	0.xxxx	0.xxxx			

^{*} Using Holm's-Bonferroni adjustment within each antigen, the p-value is statistically significant.

Programming Note: Continue Table 14.2.7.1(d) for each antigen in the following order: CFA/I, CS3, CS6, CS5, and 078 LPT. For each antigen, the Holm's-Bonferroni correction will be performed. If a p-value is statistically significant after the adjustment, a "*" will be placed next to the p-value.

TABLE 14.2.6.2(a):

Comparison of Geometric Fold Rise in IgA Titer by Antibody Lymphocyte Secretion - Adults Per Protocol Population

Programming Note: Use the same Table shell as Table 14.2.7.1(a), but use the Per Protocol population instead of the Full Analysis population.

TABLE 14.2.6.2(b):

Comparison of Geometric Fold Rise in IgA Titer by Antibody Lymphocyte Secretion - Toddlers (24 - 59 Months) Per Protocol Population

Programming Note: Use the same Table shell as Table 14.2.7.1(b), but use the Per Protocol population instead of the Full Analysis population.

TABLE 14.2.6.2(c):

Comparison of Geometric Fold Rise in IgA Titer by Antibody Lymphocyte Secretion - Young Children (12 - 23 Months) Per Protocol Population

Programming Note: Use the same Table shell as Table 14.2.7.1(c), but use the Per Protocol population instead of the Full Analysis population.

TABLE 14.2.6.2(d):

Comparison of Geometric Fold Rise in IgA Titer by Antibody Lymphocyte Secretion - Infants (6 - 11 Months) Per Protocol Population

Programming Note: Use the same Table shell as Table 14.2.7.1(d), but use the Per Protocol population instead of the Full Analysis population.

Fecal Secretion

TABLE 14.2.7.1(a):

Antibody Response (≥ 2 Fold) by Fecal Secretion IgA - Adults Full Analysis Population

TABLE 14.2.7.1(b):

Antibody Response (≥ 2 Fold) by Fecal Secretion IgA - Toddlers (24 - 59 Months) Full Analysis Population

TABLE 14.2.7.1(c):

Antibody Response (≥ 2 Fold) by Fecal Secretion IgA - Young Children (12 - 23 Months) Full Analysis Population

TABLE 14.2.7.1(d):

Antibody Response (≥ 2 Fold) by Fecal Secretion IgA - Infants (6 - 11 Months) Full Analysis Population

TABLE 14.2.7.1(e):

Antibody Response (≥ 4 Fold) by Fecal Secretion IgA - Adults Full Analysis Population

TABLE 14.2.7.1(f):

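### The 73% infant power in Section 5 is for one unadjusted 5% t-test, whereas significance is declared by Holm-Bonferroni over 18 contrasts per antigen, and under that rule the power is far lower

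*SAP*

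**What the plan says.** **Power (SAP Section 5).** "For infant cohorts, with 30 participants per group, this study is designed to provide approximately 73% power" for a 2-fold GMFR difference "between comparisons of two groups with varying doses of ETVAX and dmLT levels". The stated inputs are a "log10 standard deviation of 0.6, for CS6", taken from an earlier Swedish study of the vaccine, and a "two-sample t-test using the 5% two-sided Type I error rate and 10% drop-out rate". No allowance for multiple testing is mentioned.

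**Decision rule (Sections 6.8 and 8).** Section 6.8: "within each immunogenicity endpoint for each age group, the Holm-Bonferroni correction for multiple testing will be applied". Section 8: "For each immunogenicity endpoint and antigen analyzed, a Holm's-Bonferroni correction will be applied to determine significance".

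**Table shell.** Table 14.2.6.1(d), the infant GMFR comparison for lymphocyte-secretion IgA, lists the treatment contrasts for each antigen in three time columns. An asterisk marks a p-value only if it survives the correction; the footnote reads "Using Holm's-Bonferroni adjustment within each antigen, the p-value is statistically significant".

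**The concern.** The power sentence and the significance rule describe different procedures. The kind of comparison that Section 5 powers, two infant groups differing in ETVAX or dmLT dose, is one of the contrasts that Holm adjusts. A reader who sets the stated 73% beside a comparison without an asterisk could take it as moderate evidence against a 2-fold adjuvant or dose effect. If the rule as written misses such an effect most of the time, it is only weak evidence. The adjuvant effect of dmLT is a secondary objective (Section 3.1.2), so the stated sensitivity of that comparison should be right.

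The three descriptions of the Holm family also differ. Section 6.8 says endpoint and age group, Section 8 says endpoint and antigen, and the footnote says antigen. None says whether the three time columns of a table are corrected together or separately.

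**Working it through.** **Inputs.** From Section 5: 30 per group, 10% drop-out, hence 30 × 0.9 = 27 evaluable; effect δ = log10(2) = 0.3010; SD 0.6; two-sided α = 0.05. From Section 4.3: five infant cohorts with 10 placebos each, 50 in all, or 45 after 10% drop-out.

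**Formula.** Two-sample t-test with df = 2 × 27 − 2 = 52 and noncentrality δ / (SD × √(2/27)). Power is the probability that a noncentral t exceeds the critical value in absolute size.

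**Step 1: the plan's own figure.** Noncentrality = 0.3010 / (0.6 × 0.2722) = 1.84; critical value 2.007; power 44%. With all 30 per group it is 48%. The stated 73% is not reproduced. It would need about 54 evaluable per group, or an SD of about 0.42. For instance 0.6/√2 = 0.424 gives noncentrality 2.61 and power 72.5%. I carry both SDs below; 0.424 is back-solved and does not appear in the SAP.

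**Step 2: size of the Holm family.** Contrasts per antigen in Table 14.2.6.1(d):

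| Block | Contrasts |
|---|---|
| ETVAX doses without dmLT | 3 |
| 5 µg against 2.5 µg dmLT | 1 |
| ETVAX alone (1/2, 1/4, 1/8) against each dmLT arm | 2 + 2 + 2 = 6 |
| Placebo against each vaccine arm | 5 |
| Combined-group contrasts | 3 |
| Total | 18 |

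The first Holm threshold within one time column is 0.05/18 = 0.0028, with critical value 3.141 on 52 df.

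**Step 3: power at the first Holm step.** SD 0.6: 11%. SD 0.424: 31%.

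**Step 4: full Holm procedure.** Thresholds relax as other contrasts are rejected, so the first step alone understates the power. All 18 contrasts were simulated (2,500 trials per scenario, 27 per vaccine arm, 45 placebo). The target was 1/4 dose against 1/4 dose + 5 µg dmLT with a true 2-fold difference. Entries are unadjusted power → power under Holm.

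| Scenario | SD 0.6 | SD 0.424 |
|---|---|---|
| Only the 5 µg arm raised, 2-fold above all others | 43% → 12% | 72% → 31% |
| Both dmLT arms 2-fold up, ETVAX alone equal to placebo | 44% → 12% | 72% → 34% |
| ETVAX alone 4-fold over placebo, 5 µg arm 8-fold | 45% → 15% | 73% → 39% |
| ETVAX alone 4-fold, both dmLT arms 8-fold | 43% → 15% | 71% → 41% |

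Further runs, with placebo up to 16-fold below ETVAX alone, widen the ranges to about 11 to 17% (SD 0.6) and 31 to 43% (SD 0.424).

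**Step 5: scale of the shortfall.** Reaching 73% at 0.05/18 with SD 0.6 would take about 106 evaluable per group. This only shows the scale; it is not a proposal.

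**The case against.** Section 5 discloses its rule: one two-group comparison at 5%. Per-comparison power with its alpha stated is not in itself a miscalculation. That stands. The defect is that the figure is not tied to the rule that decides significance, and that it also fails on its own inputs.

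Four stronger readings are tempting, and the SAP does not support them.

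- *The trial was mis-sized.* Section 5 opens by saying that the sample size was chosen to detect frequent adverse events, and the primary endpoints are safety. The power sentence is secondary to that basis.
- *The asterisk is the only evidence on a dmLT or dose effect.* The shells print every raw p-value. The SAP also plans GMT ratios with unadjusted 95% confidence intervals and GMFR intervals for each arm. Section 8 sets estimation at two-sided 5%. A nominally significant effect without an asterisk would still be visible.
- *The family is 54 tests (18 contrasts × 3 time columns).* First-step power would then be 6% (SD 0.6) or 20% (SD 0.424). But Section 6.8 ties the correction to comparisons among treatment groups, which points to the contrasts and not the time columns. The text is unclear, but 54 is conjecture.
- *The Holm family must be cut down.* Narrowing it trades coverage for power, and after highest safe doses have been chosen (Section 4.4.2) it would need its own justification. The inconsistency does not require it.

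It may also be said that Section 6.8 accepts inflated Type I error. That acceptance concerns comparisons left unadjusted; within an endpoint, Holm is expressly applied.

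**Conclusion.** The point holds as a mismatch between a stated power and the decision rule. For a true 2-fold difference and 27 evaluable per group, power falls from 44% to about 11 to 17% with the printed SD, or from about 73% to about 31 to 43% with the SD that would yield the printed figure. Either way the effect misses the asterisk more often than not.

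This rests on normally distributed log fold rises with equal variance, 10% loss in every arm, a family of 18 contrasts in one time column, and the simulated response patterns.

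The gap between 73% and 11 to 17% should not all be put down to Holm: the stated inputs give only 44% before any adjustment. Correcting alpha alone, or the SD alone, would leave the sentence wrong.

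The SAP calls the immunogenicity comparisons exploratory and ties none of its own decisions to the asterisk. This is a moderate correction to a stated figure.

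**What to change.** In Section 5, correct the unadjusted power so that it agrees with the stated inputs (44% with SD 0.6 and 27 per group), or correct the SD if another value was used. Label the figure as applying to one unadjusted comparison, and add the power under the Holm rule of Section 8.

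In Section 6.8, state that the Holm family is the set of treatment contrasts within one antigen, one endpoint and one time point, and align Section 8 and the table footnotes with it.

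The cost is a few sentences and a less favourable power statement. Sample size, contrasts, estimates and data collection are unchanged.

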6 GENERAL STATISTICAL CONSIDERATIONS

6.1 General Principles

All continuous variables will be summarized using the following descriptive statistics: n (non-missing sample size), mean, standard deviation, median, quartiles and range (maximum and minimum). Where appropriate (e.g., immunogenicity), geometric means and corresponding 95% confidence intervals will be included. The number and percent of participants (based on the population sample size) of observed levels will be reported for all categorical measures. Where appropriate (e.g., immunogenicity and safety outcomes), 95% confidence intervals for the proportion of participants with an event will be included.

In general, all data will be listed, sorted by treatment and participant, and when appropriate by visit number within participant. All summary tables will be structured with a column for each treatment in the order of non-adjuvanted ETVAX, low dose adjuvanted ETVAX, medium dose adjuvanted ETVAX, high dose adjuvanted ETVAX and Placebo and will be annotated with the total population size relevant to specific tables/treatment, including any missing observations.

6.2 Timing of Analyses

The final analysis will be performed after the completion of the study. Extensive safety monitoring will be ongoing throughout the study.

6.3 Analysis Populations

A tabular listing of all participants, visits, and observations excluded from the safety, full analysis and per protocol populations will be provided in the CSR (see Listing 16.2.3).

6.3.1 Enrolled Population

All screened participants who provide informed consent (IC), regardless of the participant's randomization and treatment status in the trial, will be included in the enrolled population.

6.3.2 Safety Population

All participants in the enrolled population who receive a study vaccination and have safety data available will be included in the safety population. Treatment groups for safety analysis will be assigned according to the actual treatment received at the first vaccination. If a participant receives mixed doses (e.g., an ETVAX dose without dmLT at Dose 1 and the same ETVAX at Dose 2 with dmLT), the safety data collected after the start of the mixed dosing (e.g., post Dose 2) will be excluded from the analysis. All excluded data will be presented in the data listings. All safety analyses will be performed using this population.

6.3.3 Full Analysis Population

All participants in the enrolled population who are randomized, receive a study vaccination, and have preand/or post-vaccination immunogenicity measurements will be included in the Full Analysis (FA) Population. This population will serve as the supportive analysis population for the immunogenicity objectives.

Any additional exclusion from the Full Analysis population if warranted (e.g., a significant protocol deviation that is determined to potentially interfere with the vaccine induced immune responses) based on the blinded review of the data will be established and documented before breaking the blind.

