6.3.4 Per Protocol Population

All participants in the FA population who receive both doses of the same study vaccine and have post second dose and pre-vaccination immunogenicity measurements, with no major protocol or laboratory test standard operating procedure (SOP) violations that are determined to potentially interfere with the immunogenicity assessment of the study vaccine, will be included in the per protocol population.

The specific criteria for exclusion of participants from the PP population will be established before breaking the blind and will be based on the blinded review of protocol violations.

There could potentially be a different per protocol population for each specified sample and antigen type. Participants will be included in the sample and antigen type PP Population if they have a post second dose and pre-vaccination immunogenicity measurement for the specific sample and antigen. These populations will serve as the primary analysis populations for the immunogenicity objectives.

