6.5 Missing Data

In general, all missing data will be treated as missing completely at random and no imputation will be performed except for the safety endpoints as described below. Non-analyzable data (e.g., due to major protocol violations) will be documented in the deviations.

If some safety data are available for a participant in the FA population, but respective secondary endpoint related data are missing, then the participant will be included in the safety analysis and data will be treated as follows for immediate AEs, unsolicited AEs and serious adverse events (SAEs).

- 1. If Severity is missing for any AE, then it will be considered as an AE of maximum severity (Grade 3) "Severe", unless it is captured as SAE.
- 2. If "Relationship" is missing, then it will be considered as "Related" to the vaccine administered.
- 3. If, for Start date, the day of event/condition is missing due to any adverse event, then it will be imputed as the date of last dose of study vaccine.
- 4. If the Stop date of an adverse event is missing, then it will be treated as ongoing.

For solicited adverse events, the following assumptions will be made:

- 1. If dates are missing, but symptoms are reported, then the day post vaccination will be used to calculate the date of the symptom.
- 2. If a symptom is not reported at any time through Day 7, then no imputation for missing data will be performed. The data will be summarized as not reported on the tables.

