8.1 ALS Antibodies

For ALS IgA, tables will be presented by antigen in the order of priority as specimen volumes allow. The order of the antigens will be: LTB, CFA/I, CS3, CS6, CS5, and 078 LPS. Immune responses as measured by ALS IgA after each vaccination (Day 7 and Day 19 samples) will be evaluated by the following:

- the percentage of participants achieving an antibody response after the first vaccination (i.e., antibody response is calculated using baseline and Day 7 sample) for LTB, CFA/I, CS3, CS6, CS5 and 078 LPS (if sample available);
- the percentage of participants achieving an antibody response after the second vaccination (i.e., antibody response is calculated using baseline and Day 19 sample) for LTB, CFA/I, CS3, CS6, CS5 and 078 LPS (if sample available);
- the percentage of participants achieving an antibody response after either vaccination (i.e., antibody response observed after either vaccination) for LTB, CFA/I, CS3, CS6, CS5 and 078 LPS (if sample available);
- the geometric mean titer (GMT) of CFA/I, CS3, CS5, CS6, LTB, and 078 LPS (if sample available) at screening and after each vaccination;
- the geometric mean fold rise (GMFR) of CFA/I, CS3, CS5, CS6, LTB and 078 LPS (if sample available) between doses (baseline to post-dose 1 and post-dose 1 to post-dose 2) and from baseline to post-dose 2.

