	Use of other experimental agents within 30 days prior or after vaccination	X
	Clinically significant abnormalities in screening hematology or serum chemistry	X
	History of febrile illness wihtin 48 hours prior to vaccinatin and fever at the time of immunization)	
	Prior receipt of any cholera or ETEC vaccine	X
	Prior receipt of a blood transfusion or blood products including immunoglobulins	X
	Current use of iron or zinc supplements in 7 days prior to vaccination, current use of antacids or immunosuppressive drugs	X
	Any condition which, in the opinion of the investigator, might jeopardize the safety of study participants	X
	Receipt of antimicrobial drugs for any reason within 14 days of vaccination	X
	History of diarrhea during the 7 days prior to vaccination	X
	Culture positive for ETEC, Shigella, V. Cholerae, Salmonella or Rotavirus within 7 days of vaccination	X
	Acute disease at the time of enrollment or 3 days prior to enrollment	X
	Known or suspected impairment of immunological function	X
	Participant's parents/guardians not able, available or willing to accept weekly follow-up by study staff	X
	History of chronic administration of immunosuppressant medications	X
	Any medical condition in the parents/infants that, in the judgment of the investigator, would interfere with the study	X
	Medically significant malnutrition	X
Other	Other	X

TABLE 14.1.2(a):
Analysis Populations by Treatment Group - Adults

			cebo =XX)	Full	VAX Dose XX)	ETVAX Full Dose + 10 µg dmLT (N=XX)		All Partio	
Analysis Populations	Reason Participants Excluded	n	%	n	%	n	%	%	n
	Any Reason	X	X.X	X	X.X	X	X.X	X	X.X
Safety Population	Not Randomized/Not Vaccinated	х	X.X	X	x.x	X	x.x	X	X.X
	No Safety Data Available	X	X.X	X	x.x	X	X.X	X	X.X
	Any Reason	х	X.X	X	x.x	X	x.x	X	X.X
	Not Randomized/Not Vaccinated	х	x.x	х	x.x	X	x.x	Х	X.X
Full Analysis Population	No Valid Pre-vaccination Immunogenicity Assessment	X	X.X	X	x.x	X	X.X	X	X.X
	No Valid Post-vaccination Immunogenicity Assessment	х	x.x	х	x.x	X	x.x	Х	X.X
	Major Protocol Violation	х	X.X	X	x.x	X	x.x	X	X.X
	Any Reason	х	X.X	X	x.x	X	x.x	X	X.X
	Not Randomized/Not Vaccinated	х	x.x	х	x.x	X	x.x	Х	X.X
	Did Not Receive Both Vaccinations	х	X.X	X	x.x	X	x.x	X	X.X
Per Protocol Population	Both Vaccinations were not Same Dose	х	x.x	х	x.x	X	x.x	Х	X.X
	No Valid Pre-vaccination Immunogenicity Assessment	х	X.X	х	x.x	X	x.x	X	X.X
	No Valid Post Dose 2 Immunogenicity Assessment	х	x.x	X	x.x	X	x.x	X	x.x
	Major Protocol Violation	Х	X.X	X	X.X	X	X.X	X	X.X

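### The Full Analysis definition contradicts its own exclusion table, and Section 6.1 with the single-N shells puts participants without a derivable fold rise into the responder denominator

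*SAP*

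**What the plan says.** **Membership.** Section 6.3.3 takes randomised, vaccinated participants who "have preand/or post-vaccination immunogenicity measurements will be included in the Full Analysis (FA) Population" (the run-together word reads as pre- and/or). The Full Analysis (FA) population is secondary in rank: "This population will serve as the supportive analysis population for the immunogenicity objectives". Shells 14.1.2(a)–(d) list, under the FA population, "No Valid Pre-vaccination Immunogenicity Assessment" and its post-vaccination counterpart as reasons for exclusion.

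The Per Protocol (PP) populations of Section 6.3.4 are primary for immunogenicity and are defined by specimen and antigen: "Participants will be included in the sample and antigen type PP Population if they have a post second dose and pre-vaccination immunogenicity measurement". No Day 7 sample is required.

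**Response.** Section 8.1 says of the first dose that "antibody response is calculated using baseline and Day 7 sample". The other time points, and Sections 8.2 and 8.3, follow the same two-sample pattern.

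**Denominator.** Section 6.1: "The number and percent of participants (based on the population sample size) of observed levels will be reported for all categorical measures". It adds that summary tables are "annotated with the total population size relevant to specific tables/treatment, including any missing observations". Sections 8.1.1, 8.2.1 and 8.3.1 name no other divisor. Shells 14.2.1.1(a)–(d), and the fecal and plasma shells built on them, print one N per antigen and treatment row. Each period then has n, % and a confidence interval, with no evaluable count.

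**Missing data.** Section 6.5: "all missing data will be treated as missing completely at random and no imputation will be performed", apart from the safety endpoints. Section 8 restricts each population to participants who contributed assessments for the antigen and assay. It does not mention time point.

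**The concern.** The two descriptions of FA cannot both be programmed. A participant with a baseline sample only is in under 6.3.3 and out under shell 14.1.2.

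The denominator matters more. A participant who lacks either the baseline or that time point's result has no fold rise. If that participant stays in N, the percentage falls because a specimen is missing, not because a response was absent. The Clopper-Pearson interval and Fisher's exact test follow the same counts. Section 4.5.2 expects inadequate specimen volumes and ranks antigens for testing, so the loss could be larger for antigens low in the order. GMT and GMFR use observed values only, so they could tell a different story from the responder rate for the same arm and antigen.

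**Working it through.** No figure in the SAP depends on this point, so there is nothing to reproduce. The check sets the rules side by side and then sizes the effect.

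**Step 1: who has no derivable response but stays in N?**

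- *Baseline only, or post-vaccination only.* In FA under 6.3.3. No fold rise at any time point.
- *Baseline and Day 7, no Day 19.* In FA even under shell 14.1.2. No Day 19 fold rise. The contributor rule in Section 8 does not remove this participant, who has contributed an assessment for the antigen and assay. Repairing 6.3.3 alone is therefore not enough.
- *Baseline and Day 19, no Day 7.* In FA and in PP. No Day 7 fold rise, and the any-time result is incomplete.
- *Fecal SIgA.* Section 8.2 has two post-dose-2 samples, Day 19 and Day 29 (Day 28 in the shells). Section 6.3.4 does not say which one it requires, so the other can be missing within PP.
- *PP, ALS or plasma, Day 19.* Baseline and Day 19 are both required. No gap.

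**Step 2: size.** Let x be responders, E the evaluable participants, N the printed total and m = 1 − E/N. Then x/N = (x/E) × (1 − m).

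Assumed 60% response (not in the SAP):

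- m = 10%, the drop-out rate in Section 5: 60% × 0.90 = 54%.
- m = 20%, an assumption: 60% × 0.80 = 48%.

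In whole participants, at group sizes from Section 5, with Clopper-Pearson 95% intervals:

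| Group | Not evaluable | x/E | x/N |
|---|---|---|---|
| 30 | 3 | 16/27 = 59.3% (38.8 to 77.6) | 16/30 = 53.3% (34.3 to 71.7) |
| 30 | 6 | 14/24 = 58.3% (36.6 to 77.9) | 14/30 = 46.7% (28.3 to 65.7) |
| 15 | 2 | 8/13 = 61.5% (31.6 to 86.1) | 8/15 = 53.3% (26.6 to 78.7) |

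**Step 3: unequal missingness.** Take 30 per arm and the same assumed 70% response in both.

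- 0 and 10 not evaluable: 21/30 against 14/20 gives Fisher p = 1.00. On N, 21/30 against 14/30 gives p = 0.12.
- 1 and 8 not evaluable: 20/29 against 15/22 gives p = 1.00. On N, 20/30 against 15/30 gives p = 0.29.
- 3 and 3 not evaluable: p = 1.00 either way. Both rates fall together.

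**The case against.** The strongest reply is that the SAP never says these participants are non-responders. A printed N may be only an annotation. Section 6.5 rules out imputation, and Section 8 defines response from two samples, so a sensible programmer might divide by the evaluable count. It is true that the non-responder result is inferred. But 6.1 states a divisor, the responder sections give no exception, and the SAP does state one where it wants one: Section 9.1.1 uses participants with non-missing data for solicited-event severity, and shells 11.3.2.1 onward carry a row for the number of participants. So the rule as written conflicts with 6.5, and two programmers could defend different rates.

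Second, FA is supportive, the comparisons are declared exploratory (Section 6.8), and PP requires both samples for ALS and plasma at Day 19. This stands in full and limits the reach of the point.

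Third, the evaluable counts might be read from the GMT and GMFR tables, since Sections 8.1.2 and 8.1.3 promise the number of observations. This carries little weight: the shells for those tables footnote n as the number of participants with an antibody response, so a reader could not rely on it as the evaluable count.

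A reader might also infer that missingness differs by arm. The SAP gives no support for that. Step 3 shows only what would follow if it did.

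**Conclusion.** The contradiction between 6.3.3 and shell 14.1.2 is plain. Read literally, the denominator rule in 6.1, combined with the single-N shells, treats an underivable fold rise as non-response, against 6.5.

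The exposure covers the supportive FA responder tables at all time points. In the primary PP tables it covers Day 7, the any-time column and, for fecal SIgA, whichever of Day 19 or Day 29 is not the required post-dose-2 sample.

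Two stronger readings are not supported. The SAP does not declare such participants non-responders, and the PP Day 19 ALS and plasma responder analyses are not biased by this.

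The size is a relative fall equal to the share not evaluable: 60% to 54% at 10%, 60% to 48% at 20%. The 60% is assumed. The 10% is the drop-out rate used for power, not a stated rate of specimen failure. The change should be made before the tables are programmed, but the primary post-dose-2 ALS and plasma results do not hang on it.

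**What to change.** 1. In 6.3.3, require a valid baseline and at least one valid post-vaccination result. This matches shell 14.1.2.
2. In 8.1.1, 8.2.1 and 8.3.1, as a stated exception to 6.1, base every responder percentage, Clopper-Pearson interval and Fisher test on participants with both the baseline and that time point's result for that assay and antigen. Show this evaluable n in each period column of shells 14.2.1.1 and those built on them.
3. For the any-time column, use participants with a baseline and all scheduled post-dose results. Do not treat anyone with an observed response as evaluable, because the denominator would then depend on the outcome. For example, 9 of 12 complete participants responding is 75%. Adding only the two responders among three incomplete participants gives (9 + 2)/(12 + 2) = 11/14 = 79%.

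If a non-responder analysis is wanted, name it as a sensitivity analysis.

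The cost is SAP wording and one column per period, with no new data. Denominators become slightly smaller and intervals somewhat wider, most of all in the any-time column.
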